1.28 ADVERSE EVENTS AND SERIOUS ADVERSE EVENTS

1.28.1 Definition of Adverse Event

Adverse event means any untoward medical occurrence associated with the use of an intervention in humans, whether or not considered intervention-related (21 CFR 312.32 (a)).

1.28.2 Definition of Serious Adverse Events (SAE)

An adverse event (AE) or suspected adverse reaction is considered "serious" if, in the view of either the investigator or sponsor, it results in any of the following outcomes: death, a life-threatening adverse event, inpatient hospitalization or prolongation of existing hospitalization, a persistent or significant incapacity or substantial disruption of the ability to conduct normal life functions, or a congenital anomaly/birth defect. Important medical events that may not result in death, be life-threatening, or require hospitalization may be considered serious when, based upon appropriate medical judgment, they may jeopardize the participant and may require medical or surgical intervention to prevent one of the outcomes listed in this definition. Examples of such medical events include allergic bronchospasm requiring intensive treatment in an emergency room or at home, blood dyscrasias or convulsions that do not result in inpatient hospitalization, or the development of drug dependency or drug abuse.

1.28.3 Classification of an Adverse Event

1.28.3.1 Severity of Event

All AEs will be assessed by the study clinician using the NCI Common Terminology Criteria for Adverse Events (CTCAE) 5.0 as the protocol defined grading system.

For adverse events (AEs) not included in the protocol defined grading system, the following guidelines will be used to describe severity.

- **Mild** – asymptomatic or mild symptoms; clinical or diagnostic observations only; intervention not indicated. Such events do not interfere with the participant's daily activities.

- **Moderate** – local or non-invasive intervention indicated; limiting age-appropriate ADL Such events result in a low level of inconvenience or concern with the therapeutic measures.
- **Severe** – medically significant but not immediately life-threatening; hospitalization or prolonged hospitalization indicated; disabling; limiting self care ADL Events that interrupt a participant's usual daily activity may require systemic drug therapy or other treatment. Severe events are usually potentially life-threatening or incapacitating. Of note, the term "severe" does not necessarily equate to "serious".
-

1.28.3.2 Relationship to Study Intervention

All adverse events (AEs) must have their relationship to study intervention assessed by the investigator who examines and evaluates the participant based on temporal relationship and his/her clinical judgment. The degree of certainty about causality will be graded using the categories below. In a clinical trial, the study product must always be suspect.

- **Definitely Related** – There is clear evidence to suggest a causal relationship, and other possible contributing factors can be ruled out. The clinical event, including an abnormal laboratory test result, occurs in a plausible time relationship to study intervention administration and cannot be explained by concurrent disease or other drugs or chemicals. The response to withdrawal of the study intervention (dechallenge) should be clinically plausible. The event must be pharmacologically or phenomenologically definitive, with use of a satisfactory rechallenge procedure if necessary.
- **Probably Related** – There is evidence to suggest a causal relationship, and the influence of other factors is unlikely. The clinical event, including an abnormal laboratory test result, occurs within a reasonable time after administration of the study intervention, is unlikely to be attributed to concurrent disease or other drugs or chemicals, and follows a clinically reasonable response on withdrawal (dechallenge). Rechallenge information is not required to fulfill this definition.
- **Potentially Related** – There is some evidence to suggest a causal relationship (e.g., the event occurred within a reasonable time after administration of the trial medication). However, other factors may have contributed to the event (e.g., the participant's clinical condition, other concomitant events). Although an AE may rate only as "possibly related" soon after discovery, it can be flagged as requiring more information and later be upgraded to "probably related" or "definitely related", as appropriate.
- **Unlikely to be related** – A clinical event, including an abnormal laboratory test result, whose temporal relationship to study intervention administration makes a causal relationship improbable (e.g., the event did not occur within a reasonable time after administration of the study intervention) and in which other drugs or chemicals or underlying disease provides plausible explanations (e.g., the participant's clinical condition, other concomitant treatments).

Abbreviated Title: Liraglutide in Teens Post-SG

Version Date: 1/30/23

- **Not Related** – The AE is completely independent of study intervention administration, and/or evidence exists that the event is definitely related to another etiology. There must be an alternative, definitive etiology documented by the clinician.]

1.28.3.3 Expectedness

Expected adverse reactions are AEs that are known to occur for the study intervention being studied and should be collected in a standard, systematic format using a grading scale based on functional assessment or magnitude of reaction. The source of the reference safety information used to determine the expectedness of the AE will be the package insert (approved labeling) for liraglutide approved for adults. Expectedness is assessed based on the awareness of AEs previously observed, not on the basis of what might be anticipated from the properties of the study intervention.

The principal investigator will be responsible for determining whether an adverse event (AE) is expected or unexpected. An AE will be considered unexpected if the nature, severity, or frequency of the event is not consistent with the risk information previously described for the study intervention. These determinations will also be reviewed by the study Safety Officer.

Liraglutide administration has known adverse consequences, delineated in the SAXENDA package insert [61]. If the rate or severity of these such consequences exceeds the rate or severity anticipated in the FDA-approved package insert, the events will be classified and reported as Unanticipated Problems, but otherwise will be considered expected events that will be described and reported to the IRB and DSMB at each Continuing Review.

We also anticipate that other mild symptoms may occur in the course of participation in the protocol unrelated to study drug or participation, with mild signs/symptoms (CTCAE Grade ≤ 2), such as rhinorrhea, nasal congestion, watery eyes, cough, lightheadedness, mild wheezing, menstrual cramps, muscle weakness, fever blister, mild urinary tract infection, etc., that occur infrequently ($\leq 20\%$). These will also be summarized and reported to the IRB and DSMB at the time of Continuing Reviews.

1.28.4 Time Period and Frequency for Event Assessment and Follow-Up

The occurrence of an adverse event (AE) or serious adverse event (SAE) may come to the attention of study personnel during study visits and interviews of a study participant presenting for medical care, or upon review by a study monitor.

All AEs including local and systemic reactions not meeting the criteria for SAEs will be captured on the appropriate case report form (CRF). Information to be collected includes event description, time of onset, clinician's assessment of severity, relationship to study product (assessed only by those with the training and authority to make a diagnosis), and time of resolution/stabilization of the event. All AEs occurring while on study must be documented appropriately regardless of relationship. All AEs will be followed to adequate resolution.

Any medical condition that is present at the time that the participant is screened will be considered as baseline and not reported as an AE. However, if the study participant's condition deteriorates at any time during the study, it will be recorded as an AE.

Abbreviated Title: Liraglutide in Teens Post-SG

Version Date: 1/30/23

Changes in the severity of an AE will be documented to allow an assessment of the duration of the event at each level of severity to be performed. AEs characterized as intermittent require documentation of onset and duration of each episode.

The principal investigator or associate investigators will record all reportable events with start dates occurring any time after informed consent is obtained until 7 (for non-serious AEs) or 30 days (for SAEs) after the last day of study participation. At each study visit, the investigator will inquire about the occurrence of AE/SAEs since the last visit. Events will be followed for outcome information until resolution or stabilization.

1.28.5 Adverse Event Reporting

Events occurring during this study will be reported to the NIH IRB per policy 801.

The Safety Officer monitoring this trial and the NICHD Clinical Director will also be sent reports of all Reportable Events following the same timelines as required for IRB reporting.

We anticipate that mild symptoms may occur in the course of participation in the protocol unrelated to study drug or participation, with mild signs/symptoms (CTCAE Grade ≤ 2), such as rhinorrhea, nasal congestion, watery eyes, cough, lightheadedness, mild wheezing, menstrual cramps, muscle weakness, fever blister, mild urinary tract infection, etc., that occur infrequently ($\leq 20\%$). These will be summarized and reported at Continuing Review.

1.28.6 Serious Adverse Event Reporting

Events occurring during this study will be reported to the NIH IRB per policy 801.

Each patient must be carefully monitored for the development of any AEs. This information should be obtained in the form of non-leading questions (e.g., “How are you feeling?”) and from signs and symptoms detected during each examination, observations of study personnel, and spontaneous reports from participants.

All AEs (serious and non-serious) spontaneously reported by the patient and/or in response to an open question from study personnel or revealed by observation, physical examination or other diagnostic procedures will be recorded on the appropriate CRF. Any clinically relevant deterioration in laboratory assessments or other clinical findings is considered an AE and must be recorded on the appropriate CRF. When possible, signs and symptoms indicating a common underlying pathology should be noted as one comprehensive event.

The study Principal Investigator will report to the NICHD Clinical Director any serious adverse event, whether or not considered study intervention related, including those listed in the protocol or investigator brochure and must include an assessment of whether there is a reasonable possibility that the study intervention caused the event within 24 hours from the point in time when the Investigator becomes aware of the SAE. Study endpoints that are serious adverse events (e.g., all-cause mortality) must be reported in accordance with the protocol unless there is evidence suggesting a causal relationship between the study intervention and the event (e.g., death from anaphylaxis).

All serious adverse events (SAEs) will be followed until satisfactory resolution or until the site investigator deems the event to be chronic or the participant is stable. Other supporting documentation of the event may be requested by the NICHD Clinical Director and should be provided as soon as possible.

Abbreviated Title: Liraglutide in Teens Post-SG

Version Date: 1/30/23

The study Principal Investigator will be responsible for notifying the Food and Drug Administration (FDA) of any unexpected fatal or life-threatening suspected adverse reaction as soon as possible, but in no case later than 7 calendar days after the PI's initial receipt of the information. In addition, the PI must notify FDA and all participating investigators in a safety report of potential serious risks, from clinical trials or any other source, as soon as possible, but in no case later than 15 calendar days after the PI determines that the information qualifies for reporting.

All serious adverse events will be reported by the PI verbally and in writing as soon as possible to the NICHD Clinical Director. All adverse events (serious and non-serious, expected and unexpected) will be reported annually to the IRB and NICHD Clinical Director for review. Electronic data sheets or summary language will be supplied for IRB review of adverse event reports at continuing reviews.

The PI (**[name], PhD**) will report adverse events in iRIS, to the IRB and to the NICHD Clinical Director in writing.

1.28.7 Events of Special Interest

None expected.

1.28.8 Reporting of Pregnancy

The effects of liraglutide on the unborn child and on the newborn baby are not known. Thus, it is important that participants do not become pregnant during the course of the study. Females with child-bearing potential will be required to undergo a pregnancy test prior to starting the study. Pregnancy testing will be monitored during the study. Males will also be instructed not to father a child for at least 6 months after completion of the study. Those who are sexually active and not surgically sterile must use effective contraception. If a female participant were to become pregnant during the study, she would be instructed to discontinue the study intervention and would end study-related visits. We would however contact the participant to ascertain the outcome of the pregnancy. If a male participant were to father a child during the study, the mother of his child would be recommended to have close clinical obstetric follow-up.

1.29 UNANTICIPATED PROBLEMS

1.29.1 Definition of Unanticipated Problems (UP)

Any incident, experience, or outcome that meets all of the following criteria:

- Unexpected in terms of nature, severity, or frequency given (a) the research procedures that are described in the protocol-related documents, such as the Institutional Review Board (IRB)-approved research protocol and informed consent document; and (b) the characteristics of the participant population being studied; and
- Related or possibly related to participation in the research (“possibly related” means there is a reasonable possibility that the incident, experience, or outcome may have been caused by the procedures involved in the research); and
- Suggests that the research places participants or others (which many include research staff, family members or other individuals not directly participating in the research) at a

Abbreviated Title: Liraglutide in Teens Post-SG

Version Date: 1/30/23

greater risk of harm (including physical, psychological, economic, or social harm) than was previously known or expected.

1.29.2 Unanticipated Problem Reporting

The investigator will report unanticipated problems (UPs) to the NIH Institutional Review Board (IRB) as per Policy 801.

1.29.3 NIH Intramural IRB Reporting of IND Safety Reports

Only IND Safety Reports that meet the definition of an unanticipated problem will need to be reported to the NIH Intramural IRB.

STATISTICAL CONSIDERATIONS

1.30 STATISTICAL HYPOTHESIS

- Primary Endpoint:

The Primary Endpoint is estimation of required sample size for a later RCT through calculation of effect size for change in body mass index (BMI) from baseline to 16 weeks of liraglutide. The hypothesis is: The data will be sufficient to calculate the effect size for change in BMI from baseline to 16 weeks for a 2-group experiment (placebo versus liraglutide).

- Secondary Endpoint(s):

There are 3 sets of key secondary endpoints:

- A. Changes in BMI and fat mass after 16 weeks of liraglutide.
- B. Comparison of changes in BMI and fat mass after 16 weeks liraglutide in participants who had a poor initial response to SG (<20% BMI reduction at BMI nadir) vs. those with a typical post-SG weight loss ($\geq 20\%$ BMI reduction at BMI nadir)
- C. Tolerability and safety of 3.0 mg Liraglutide

Statistical hypothesis A: there will be a statistically significant decrease in BMI and fat mass after 16 weeks of liraglutide.

Statistical hypothesis B: there will be a statistically significant greater decrease in BMI and fat mass after 16 weeks of liraglutide in participants in who had a typical post-SG weight loss vs. those who had a poor initial response to SG.

1.31 SAMPLE SIZE DETERMINATION

As this is a pilot investigation to determine the sample size of a fully powered investigation, no formal sample size determination is necessary. That said, the study is powered such that it might be able to detect a moderate-to-large difference from treatment. A recent randomized, double-blind, placebo-controlled phase 3 trial of liraglutide for adolescents (age 12 to <18 years) with obesity ($BMI \geq 30 \text{ kg/m}^2$ and $\geq 95^{\text{th}}$ percentile for age and sex) [32] reported a -1.39 kg/m^2 ($SE=0.31$, $n=125$) difference over 1 year of liraglutide treatment. If that effect size is replicated and if a similar SD (3.46) is found in the present study, we estimate that a total sample size of 40 subjects will have 80% power (β) to detect a -1.39 kg/m^2 difference in BMI (effect size = -

Abbreviated Title: Liraglutide in Teens Post-SG

Version Date: 1/30/23

0.4017) at level of significance of 0.05 (1-sided, as we are interested only in BMI loss). See **Table 2**.

t-test - Means: Difference between two dependent means (matched pairs) Tails = 1, $\alpha = 0.05$, Effect size dz = 0.4

[figure not shown]

Table 2, drawn using data obtained using G-Power 3.1.9.2 [90, 91]

We anticipate that virtually all participants who sign consent and are screened will qualify and agree to enroll. We will therefore attempt to recruit and screen in person no more than 50 adolescents, among whom no more than 43 will be treated with liraglutide in hopes of having 40 who complete the study. Based on prior studies in adolescents using liraglutide, we anticipate few dropouts or withdrawals by week 16. In Kelly et al's study of adolescents [32], 119/125 (95%) of those treated with liraglutide remained on-treatment at week 16.

As a pilot investigation, there is no assumption that there will be adequate power for any of the secondary outcomes investigated. We will, however, be able to use the data to determine power in a future randomized controlled trial for these outcomes.

1.32 POPULATIONS FOR ANALYSES

The following analysis populations will be evaluated and used for presentation and analysis of the data:

- **Screening Analysis** Dataset: All participants who have a signed informed consent form.
- **Intention-to-Treat (ITT) Analysis** Dataset: all treated participants. The ITT Population will consist of all adolescent subjects who were assigned to treatment regardless of whether the subject received treatment or not. A subject is considered assigned to treatment when the Investigator or Investigator's designee assigns a medication study number. For all analyses in the ITT Population, participants will be analyzed as treated, whether or not treatment was received.
- **Safety Analysis** Dataset: the subset of participants for whom safety analyses will be conducted: Participants who took at least one dose of study medication will be considered part of the Safety Analysis Dataset.

Abbreviated Title: Liraglutide in Teens Post-SG

Version Date: 1/30/23

- **Per Protocol Dataset:** Those who complied with the protocol sufficiently to ensure that these data would be likely to represent the effects of treatment according to the underlying scientific model (i.e., participants who took at least 80% of study intervention for 80% of the days within the treatment period).

1.32.1 Evaluable for toxicity

All participants will be evaluable for toxicity from the time of their first treatment with liraglutide.

1.32.2 Evaluable for objective response

Not applicable

1.32.3 Evaluable Non-Target Disease Response

Not applicable

1.33 STATISTICAL ANALYSES

1.33.1 General Approach

Tabulations will be produced for appropriate demographic, baseline, efficacy, and safety parameters. For categorical variables, summary tabulations of the number and percentage of subjects within each category of the parameter will be presented. For continuous variables, the number of subjects (N), mean, median, standard deviation (SD), minimum, and maximum values will be presented.

Formal statistical hypothesis testing will be performed on endpoints with testing conducted at the 1-sided, 5% level of significance. Summary statistics will be presented, as well as confidence intervals (Cis), as described in the sections below. Trial success will be based on a p-value <0.05.

Covariates to be modeled are pre-specified in the sections below. Results of statistical procedures for efficacy outcomes involving covariates will be presented as adjusted means (least-squares means) with standard errors.

Checks of assumptions (e.g., normality) underlying statistical procedures will be performed and corrective procedures will be applied. It is expected that log transformation will be used for the primary outcome and most secondary outcomes. Percentage data will be arcsin (square root (value)) transformed for analysis.

Unless otherwise noted, all statistical analyses will be performed using SPSS statistical software Version 25 (IBM Corp, Armonk, NY) or higher.

Subject disposition will be tabulated and include the number screened, the number randomized, the number treated in total, the number dosed with liraglutide, the number in each subject population for analysis, and the number who withdrew prior to completing the study and reason(s) for withdrawal.

A by-subject data listing of study completion information including the reason for premature study withdrawal, if applicable, will be made available. Subject disposition will include patients in the Screening Analysis Dataset.

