1.26.3 Correlative Studies for Research/Pharmacokinetic Studies

Blood samples will be collected for secretome analysis by SomaScan [87] (10 mL at baseline and follow-up) and for future research (20 mL). For SomaScan, obtained serum will be immediately stored at -80°C until further analysis without being exposed to freeze-thaw cycles. Serum proteomic analysis will use the SOMAscan 1.3k Assay (SomaLogic, Boulder, CO). This aptamer-based assay can detect 1305 protein analytes in human serum.[88] The proteins quantified include cytokines, hormones, growth factors, receptors, kinases, proteases, protease inhibitors, and structural proteins. A complete list of analytes measured can be found at <http://somalogic.com/wp-content/uploads/2017/06/SSM-045-Rev-2-SOMAscan-Assay-1.3k-Content.pdf>. Concentrations are measured as Relative Fluorescence Units. The assay will be performed according to manufacturer specifications, with data inspection using a web tool, as previously described.[89].

Abbreviated Title: Liraglutide in Teens Post-SG

Version Date: 1/30/23

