1.33.3 Analysis of the Secondary Endpoint(s)

There are 2 sets of key secondary endpoints. These analyses are not dependent on findings of the primary endpoint. They will be calculated as changes from baseline to 16-week visit in the ITT dataset:

1. Changes in BMI and fat mass after 16 weeks of liraglutide.
2. Comparison of changes in BMI and fat mass after 16 weeks of liraglutide in participants who had a poor initial response to SG (<20% BMI reduction at BMI nadir) vs. those with a typical post-SG weight loss ($\geq 20\%$ BMI reduction at BMI nadir)

For these analyses, last observation carried forward (LOCF) imputation will be used for missing data. The sample is too small to use any other statistical imputation method accurately. A sensitivity analysis using baseline observation carried forward (BOCF) will also be conducted.

Changes in BMI and fat mass after 16 weeks of liraglutide will be evaluated using paired t-tests of baseline versus 16-week values. Data will be transformed as necessary to meet statistical assumptions of normality.

Comparisons between those who had a poor versus typical post-SG weight loss will be conducted with ANCOVAs with change (16-week minus baseline value) as the dependent factor; group (poor vs. typical weight loss) as the independent factor; and sex, race, age, and height tested as potential covariates.

Tertiary endpoints will be evaluated using similar approaches. For the secretome analysis, paired statistical tests will be applied to each analyte (using parametric or nonparametric statistical approaches as required by the data) to find significant changes in secretome components. The Benjamini-Hochberg procedure will be used to determine the false discovery rate for multiple comparisons.

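### The one-sided 5% rule exempts no endpoint; the 1,305 secretome tests and the exploratory tests with no stated direction should be expressly two-sided

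*Combined protocol and SAP*

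**What the plan says.** Section 1.33.1 sets one rule for the trial: "Formal statistical hypothesis testing will be performed on endpoints with testing conducted at the 1-sided, 5% level of significance". It makes no exception.

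The reason for one-sided testing appears once, in the sample size section (1.31): "1-sided, as we are interested only in BMI loss". Section 1.30 gives two directional statistical hypotheses. Hypothesis A is that "there will be a statistically significant decrease in BMI and fat mass after 16 weeks of liraglutide". Hypothesis B is that the fall in the same two measures is larger in typical than in poor responders to surgery. No other endpoint is given a direction.

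Testing nevertheless extends further. Section 1.33.3 says: "Tertiary endpoints will be evaluated using similar approaches". For the secretome it plans a paired test on each analyte "to find significant changes in secretome components", and adds: "The Benjamini-Hochberg procedure will be used to determine the false discovery rate for multiple comparisons". No false discovery level is given. Section 1.26.3 gives the number of analytes: "This aptamer-based assay can detect 1305 protein analytes in human serum". Section 1.33.9 is mainly descriptive. It allows unadjusted paired t-tests on a list that includes PYY, physical activity, Beck score, C-SSRS, body esteem, lipids and SomaScan. Neither 1.33.3 nor 1.33.9 states a side, and two-sided testing is mentioned nowhere in the statistical sections.

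**The concern.** A one-sided test needs a direction chosen beforehand. For BMI and fat mass the plan gives one, and that choice is not questioned here. For the proteins, PYY, activity, Beck score, C-SSRS and body esteem it gives none. The objectives table describes activity and the psychological measures in neutral terms.

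Nor can the direction be taken for granted. The adverse-reaction table in Section 1.17.2.2 shows depression (4.0% versus 2.4%) and dyslipidemia (4.8% versus 3.2%) more often on liraglutide than on placebo, so a worsening in Beck score or lipids is conceivable.

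The text can be read in two ways. On its face, the one-sided rule covers all these tests, and each needs a side that the plan does not supply. If *Formal* is meant to exclude exploratory work, their sidedness is stated nowhere, and the analyst's choice changes a p-value by a factor of two. On either reading, which secretome and exploratory changes are called significant depends on a decision not made in advance.

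**Working it through.** **1. The plan's own figure.** Section 1.31 gives a mean BMI change of -1.39 kg/m², SD 3.46, N = 40, one-sided 0.05 and 80% power. The effect size is 1.39 / 3.46 = 0.4017. Paired t-test power is the probability that a noncentral t with n - 1 = 39 df and noncentrality d√n exceeds the critical value t(0.95, 39).

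- One-sided, d = 0.4017: power 80.3%, required N = 40. The plan's figure reproduces.
- Two-sided: power 69.8%, required N = 51. The plan's figure is therefore one-sided.
- The RCT example in Section 1.33.2 (d = 0.4566) also reproduces one-sided: 60 per group, 120 in total.

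**2. A single test with no stated direction.** Same formula, n = 40, for a true change of d SDs:

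| d | One-sided, true change on the other side | Two-sided | One-sided, right side |
|---|---|---|---|
| 0.3 | 0.022% | 45.7% | 58.7% |
| 0.4 | 0.0018% | 69.4% | 80.0% |
| 0.5 | 0.0001% | 86.9% | 92.8% |

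At d = 0.4 the result is similar across plausible sample sizes. With n = 34 it is 0.004% versus 62.0%, and with n = 43 (the maximum treated) it is 0.001% versus 72.7%.

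**3. Side taken from the data.** The reported p-value is then half the two-sided one, so a nominal 5% test has a true error of 2 × 5% = 10%. If none of the 1,305 proteins changed, unadjusted false positives would rise from 1,305 × 0.05 = 65 to 1,305 × 0.10 = 130.5.

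**4. Effect on Benjamini-Hochberg.** Halving every p-value and applying the procedure at level q is the same as applying it to two-sided p-values at 2q. For independent tests the false discovery rate (FDR) is q × (share of proteins unchanged). With an assumed q = 0.05 and 10% of proteins changed, this gives 0.05 × 0.90 = 4.5% two-sided and 0.10 × 0.90 = 9.0% with the side taken from the data.

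A simulation agrees. It used 1,305 proteins, n = 40, 200 runs per setting, and changed proteins split equally between rises and falls. The FDR level, the shares changed and the effect sizes are assumptions, because the plan gives none of them.

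- q = 0.05, 5% to 20% changed by 0.5 to 1.0 SD: FDR 4.0% to 4.9% two-sided, 8.0% to 9.9% with the side from the data.
- q = 0.10: 7.9% to 9.7% versus 15.9% to 19.8%.
- Central case (q = 0.05, 10% changed, 0.8 SD): FDR 4.5% versus 9.1%, or 6.1 versus 13.0 false proteins on average.
- Proteins correlated 0.5 in blocks of 29 (300 runs): 4.6% versus 9.2%.
- No protein changed (20,000 runs), q = 0.05: chance of any false discovery 4.8% versus 9.7%.

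**5. One side fixed for all proteins.** In the central case, testing only for decreases finds 48.9% of true changes, against 97.8% two-sided, and none of the increases. If 10% of the changed proteins rise it finds 89.0%; if 90% rise it finds 9.2%.

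**The case against.** The strongest reply is that Section 1.33.1 speaks of *formal* testing and goes on to define trial success by a p-value. That is the language of stated hypotheses, of which there are only A and B. Section 1.33.9 treats exploratory work as descriptive, with tests optional and read in the light of how many are done. On this view the one-sided rule already stops where it should. The phrase about similar approaches may refer only to paired tests, ANCOVA and transformations. Looking for changes in the secretome suggests two-sided testing. Nothing in the plan fixes a decrease for every protein or lets the side follow the data, so the figures above show the cost of a misuse, under assumed settings. A side fixed in advance would still control the FDR.

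The adverse-reaction figures are also thin. Depression is about 5 of 125 versus 3 of 126, and dyslipidemia about 6 versus 4 (Fisher p about 0.50 and 0.54). They say nothing about mean scores or mean lipids. Worsening mood is caught by same-day scoring and follow-up of Beck and C-SSRS (Section 1.27), not by a t-test. Finally, this is an uncontrolled pilot whose Section 1.31 disclaims adequate power for secondary outcomes, and no decision rule uses these labels.

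Much of this limits the consequences, and it is accepted. The adverse-reaction table shows only that worsening is possible. It does not remove the point. The narrower reading leaves the sidedness of these tests unstated, while the plan still calls analytes significant and passes their p-values to Benjamini-Hochberg. An analyst who used two-sided output would depart from the plain words of Section 1.33.1.

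**Conclusion.** The concern holds and should be corrected. The written rule is one-sided for endpoints generally, but its justification and stated directions reach only BMI and fat mass. Applied to tests without a direction, it either makes opposite changes practically undetectable (0.002% versus 69% at 0.4 SD, n = 40) or, if the side follows the data, doubles the per-test error and roughly doubles the secretome FDR.

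The doubling follows from halving the p-values and does not depend on the simulation settings. The FDR percentages and counts of false proteins do depend on the assumed q, effect sizes, shares changed and correlation. The share of true changes missed under a fixed side depends mainly on how many proteins move the other way.

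The consequence is confined to which exploratory and secretome changes are called significant. Hypotheses A and B, the primary endpoint, N = 40, the safety summaries and the effect sizes and SDs carried to the RCT are unaffected. Section 1.31 intends to use the data "to determine power in a future randomized controlled trial for these outcomes", and that rests on effect sizes and SDs, not on these p-values. Descriptive results would still show any worsening.

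**What to change.** - **Section 1.33.1:** limit one-sided 5% testing to hypotheses A and B (BMI and fat mass) and to any adiposity measure, such as body weight, BMIZ or percentage fat, for which the plan states the same direction in advance. Name these measures, because body weight and BMIZ are secondary in the objectives table but exploratory in the synopsis and Section 1.33.9.
- **Section 1.33.3:** state that each secretome analyte is tested two-sided and that the two-sided p-values enter Benjamini-Hochberg.
- **Section 1.33.9:** state that all other exploratory tests use two-sided p-values with two-sided 95% confidence intervals.

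The cost is one sentence in each section, with no new data and no change to N = 40. Exploratory tests with an implied direction, such as energy intake, lose some power at n = 40: 80% to 69% at 0.4 SD, 59% to 46% at 0.3 SD, and 93% to 87% at 0.5 SD. Stating a direction in advance for such an endpoint would also remove the ambiguity for that endpoint, but this is not workable for 1,305 proteins.
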